8.2.4 Duration

For both AEs and SAEs, the investigator will provide a record of the start and stop dates of the event.

8.2.5 Action Taken

The investigator will report the action taken with IP as a result of an AE or SAE, as applicable (e.g., discontinuation or reduction of IP, as appropriate) and report if concomitant and/or additional treatments were given for the event.

8.2.6 Outcome

All SAEs that have not resolved upon discontinuation of the subject's participation in the study must be followed until recovered, recovered with sequelae, not recovered (death due to another cause) or death (due to the SAE).

8.2.7 Abnormal Laboratory Values

An abnormal laboratory value is considered to be an AE if the abnormality:

- · results in discontinuation from the study;
- · requires treatment, modification/ interruption of IP dose, or any other therapeutic intervention: or
- · is judged to be of significant clinical importance

Regardless of severity grade, only laboratory abnormalities that fulfill a seriousness criterion need to be documented as an SAE.

If a laboratory abnormality is one component of a diagnosis or syndrome, then only the diagnosis or syndrome should be recorded on the AE page/screen of the eCRF. If the abnormality was not

a part of a diagnosis or syndrome, then the laboratory abnormality should be recorded as the AE.

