1.3.2 Secondary Endpoints

The secondary endpoints are:

- 1.3.2.1 Safety (type, frequency, severity of AEs and relationship of AEs to SGI-110)
- 1.3.2.2 Overall response rate
- 1.3.2.3 Duration of remission
- 1.3.2.4 Incidence of acute and chronic graft versus host disease (GVHD)
- 1.3.2.5 Overall survival and disease free survival at one year after study enrollment

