RICAZA study Investigators conducted a study using subcutaneous azacitidine in 27 AML patients who had undergone reduced-intensity conditioning (RIC) allogeneic stem cell transplantation (19). The conditioning regimen was fludarabine, melphalan, and alemtuzumab, and the azacitidine regimen consisted of 36 mg/m2 for 5 consecutive days every 28 days for up to 10 cycles. The median time to start of azacitidine treatment was 64 days after the allogeneic stem cell transplantation. An additional 19 patients enrolled as the control group, received the same conditioning regimen, but no maintenance therapy. The investigators found that 3 of the 27 patients who received maintenance therapy developed grade 2 acute GVHD, and none developed grade 3e4 GVHD. Two patients developed limited chronic GVHD of the skin, and none developed chronic extensive GVHD. In comparison, the control group had a higher GVHD rate, with 7 of 19 developing grade 2 acute GVHD and 7 of 19 chronic GVHD. Despite these encouraging results, 7 of the 27 patients relapsed at a median of 6 months after transplantation.

Decitabine is another epigenetic therapy that has been investigated in the post-transplant maintenance setting (20). The maximum tolerated dose (MTD) was defined as the maximum dose at which $\leq 25\%$ of people experience dose-limiting toxicities during the first cycle of treatment. Twenty-four patients were enrolled and 22 were evaluable. All 4 dose levels were completed and no MTD was reached. Overall, decitabine maintenance was well tolerated. Grade 3 and 4 hematological toxicities were experienced by 75% of patients, including all patients treated at the highest dose level. Nine patients completed all 8 cycles and 8 of them remain in CR. Nine patients died from relapse (n = 4), infectious complications (n = 3), and GVHD (n = 2). Most occurrences of acute GVHD were mild and resolved without interruption of treatment; 1 patient died of acute gut GVHD. In conclusion, decitabine maintenance is associated with acceptable toxicities when given in the post-allo transplantation setting.

Despite the encouraging results reported, pre-emptive strategies, to prevent relapse, including pharmacological, immunological and cellular therapies pose the dilemma of administering potentially toxic therapy without evidence of relapse. Therefore patient selection for the right group of patients to be included in those studies is very important.

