4.4.1 Hematologic Toxicity

4.4.1.1 Cohort 1:

- 4.4.1.1.1 No dose reductions, delays or modifications are required for hematologic toxicities during the treatment cycles given with an intent to achieve CR/CRi. It is assumed that low counts observed in the presence of active disease (no morphological remission) are due to involvement by the disease and require treatment for improvement. Patients will not require dose modifications for hematological toxicity before they are reported to achieve morphological remission.
- 4.4.1.1.2 For patients who achieve complete morphological remission (CR/CRi) on study, they will receive the subsequent cycles (given as maintenance therapy) approximately every 28 days, provided that their peripheral blood counts have recovered (ANC>=1.0 X 10⁹ /L and platelet count>=50 X 10⁹/L)). If the peripheral count recovery is delayed beyond 42 days from Day 1 of the prior cycle and the delay is presumed to be secondary to therapy (after confirmation of achieving morphological remission), the SGI-110 doses may be reduced at least by one level for subsequent doses (e.g. from 40 to 30 mg).

4.4.1.2 Cohort 2:

- 4.4.1.2.1 No dose reductions, delays or modifications are required for hematologic toxicities during the treatment cycles given in the continuous presence of MRD. It is assumed that low counts in the presence of MRD are due to disease involvement and require treatment for improvement. Indeed, the dose level of SGI-110 can be increased at least one dose level at the discretion of treating physician and principal investigator if persistency of MRD is documented at any time point of disease assessment while on study independent of hematological toxicities observed as indicated at 4.2.2.4.
- 4.4.1.2.2 After the documentation of MRD negative status with the SGI-110 treatment, if the peripheral count recovery is delayed beyond 42 days from Day 1 of the prior cycle and the delay is presumed to be secondary to therapy, the SGI-110 doses may be reduced at least by one level for subsequent doses (e.g., from 30 to 20 mg).
- 4.4.1.3 Cohort 3: If the peripheral count recovery is delayed beyond 42 days from Day 1 of the prior cycle and the delay is presumed to be secondary to therapy, the SGI-110 doses may be reduced at least by one level for subsequent doses (e.g., from 30 to 20 mg).

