5.0 Evaluation During Study

- 5.1 Evaluations during SGI-110 cycles
 - 5.1.1 To be done within 72 hours of each cycle and if clinically indicated, on the third day of each cycle and once per week in the second and third week of each cycle: CBC, differential, platelet, SGPT, bilirubin, creatinine, electrolytes, serum or urine pregnancy test for women with reproductive potential.

Other laboratory tests can be performed as medically indicated.

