8.2.2 Severity / Intensity

The severity / intensity of AEs will be graded based upon the subject's symptoms according to the currently active minor version of Common Terminology Criteria for Adverse Events (CTCAE, Version 4.0).

AEs that are not defined in the CTCAE should be evaluated for severity according to the following scale:

- Grade 1 = Mild transient or mild discomfort; no limitation in activity; no medical intervention/therapy required
- Grade 2 = Moderate mild to moderate limitation in activity, some assistance may be needed; no or minimal medical intervention/therapy required

- Grade 3 = Severe marked limitation in activity, some assistance usually required; medical intervention/therapy required, hospitalization is possible
- Grade 4 = Life threatening extreme limitation in activity, significant assistance required; significant medical intervention/therapy required, hospitalization or hospice care probable
- Grade 5 = Death the event results in death

The term "severe" is often used to describe the intensity of a specific event (as in mild, moderate or severe myocardial infarction); the event itself, however, may be of relatively minor medical significance (such as severe headache). This criterion is *not* the same as "serious" which is

based on subject/event *outcome* or *action* criteria associated with events that pose a threat to a subject's life or functioning.

Seriousness, not severity, serves as a guide for defining regulatory obligations.

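### Laboratory AEs are defined by action or judgment, not by grade, so some grade 3-4 cytopenias need not reach the safety endpoint

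*Combined protocol and SAP*

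**What the plan says.** The safety endpoint in section 1.3.2.1 is "Safety (type, frequency, severity of AEs and relationship of AEs to SGI-110". It counts AEs, so whatever is not an AE is outside it.

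Section 8.2.7 sets the entry rule for laboratory values: "An abnormal laboratory value is considered to be an AE if the abnormality" meets one of three conditions. It must cause discontinuation from the study; or it "requires treatment, modification/ interruption of IP dose, or any other therapeutic intervention"; or it must be judged clinically important. None of the three is a toxicity grade.

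Section 4.4.1 says when low counts lead to a dose action:

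- Cohort 1 with active disease: "No dose reductions, delays or modifications are required for hematologic toxicities during the treatment cycles given with an intent to achieve CR/CRi". Section 4.4.1.2.1 has a parallel rule for cohort 2 while MRD persists. Both presume that the low counts come from the disease.
- Cohorts 1 and 2 after response, and cohort 3: the dose may be reduced "If the peripheral count recovery is delayed beyond 42 days from Day 1 of the prior cycle" and the delay is presumed to be due to therapy.

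Section 4.5.2.1 requires ANC of at least 1.0 x 10⁹/L and platelets of at least 50 x 10⁹/L before each maintenance cycle, which for cohort 3 means from cycle 2.

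Section 8.1 restricts the AE page to related AEs and SAEs. Sections 7.1 and 7.2 list safety among the secondary outcomes to be tabulated and do not mention graded laboratory data.

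**The concern.** Myelosuppression is the first risk of SGI-110 named in section 2.5. Tolerability in cohort 3 is a stated aim at the end of the section 2.0 background, which also asks that a maintenance agent have little or no myelotoxicity. For that toxicity, the AE rule measures how often someone intervened or thought the value important, not how low the counts fell. Two patients with the same nadir can be recorded differently because one was transfused and the other was not. At stake is the interpretation of a secondary endpoint on the drug's main expected harm, in a setting where the protocol itself often requires no dose action.

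**Working it through.** The plan gives no figure to reproduce. The check is whether a grade 3-4 low count can pass through every rule without becoming an AE.

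**Step 1: dose-related triggers by setting**

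| Setting | Dose reduction for low counts | Next cycle held for low counts |
|---|---|---|
| Cohort 1 before CR/CRi | Not required (4.4.1.1.1) | Not required (4.4.1.1.1) |
| Cohort 2 while MRD persists | Not required (4.4.1.2.1) | Not required (4.4.1.2.1) |
| Cohorts 1 and 2, maintenance | Optional, after 42 days (4.4.1.1.2, 4.4.1.2.2) | Yes, if below the 4.5.2.1 limits |
| Cohort 3, cycle 2 onward | Optional, after 42 days (4.4.1.3) | Yes, if below the 4.5.2.1 limits |

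In every row, treatment of the low count, discontinuation and clinical judgment remain as routes to an AE.

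**Step 2: two paths through the rules**

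- Cohort 3: counts fall mid-cycle, no transfusion or growth factor is given, and counts are above the 4.5.2.1 limits by day 28. The 42-day condition is not reached and the next cycle is not held. Only the judgment condition is left.
- Cohort 1 or 2 before response: counts are low, even at the start of the next cycle, and no treatment is given for them. No dose change or delay is required. Again only judgment is left.

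**Step 3: is the value recovered elsewhere?** Section 4.4 monitors hematologic toxicity with CTCAE v4.0 as a grading guide, but no text carries those grades into the analysis. Section 7 plans no graded laboratory table. The value is lost to the endpoint unless an investigator chose to enter it.

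**Step 4: a separate route to the same loss.** A low count that does qualify as an AE must still be related, or serious, to be recorded (8.1). Section 4.4.1 presumes low counts in active disease or MRD are due to disease. An AE so attributed and not serious is not recorded. The recording grid in section 8.2.1 appears to keep unrelated grade 3-5 events in Phase II, which does not agree with 8.1. Settling that conflict would not help a value that never became an AE.

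**Step 5: what could be derived.** The panel in section 5.1.1 is "CBC, differential, platelet, SGPT, bilirubin, creatinine, electrolytes", which supplies ANC, platelets, hemoglobin, ALT, bilirubin and creatinine. The wording can be read as making the day 3 and week 2-3 samples conditional on clinical indication, so some nadirs may not be measured at all.

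**Step 6: size.** Recorded rate = true rate x share captured. The documents give neither factor for SGI-110 in these cohorts, so the shortfall cannot be calculated.

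**The case against.** The strongest reply is that the gap is narrow and the definition deliberate. A transfusion or growth factor given for a low count is treatment, a held maintenance cycle is an interruption, and the judgment condition is open in every cohort. Section 4.4.1 says that dose changes are not required; it does not forbid them. Safety is secondary, and no stopping rule in section 7 uses an AE rate. All of this stands. It limits the point to the untreated low count that holds no cycle and is not judged important, but it does not close that gap.

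Four stronger readings are tempting and are not supported:

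- *That action on low counts is waived.* Only dose action is waived or deferred. In maintenance and cohort 3 the cycle-start limits still apply, so the exposure is greatest in cohorts 1 and 2 before response.
- *That the undercount is established and can be sized.* Taking 75% as the true rate and an assumed capture of 25% to 100%, cohort 3 would record 40 x 0.75 x 0.25 = 7.5 to 40 x 0.75 x 1 = 30 patients. That range only restates the assumption.
- *That the result cannot be set beside the decitabine maintenance study*, of which section 2.0 says "Grade 3 and 4 hematological toxicities were experienced by 75% of patients, including all patients treated at the highest dose level". The documents do not say how that study ascertained toxicity, and section 7 plans no such comparison.
- *That section 8.2.2 excludes laboratory grading* because AEs "will be graded based upon the subject's symptoms". The same sentence goes on to require CTCAE v4.0, so this is loose wording only.

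**Conclusion.** The point holds as a risk of under-ascertainment. Under 8.2.7 a grade 3-4 cytopenia enters the safety endpoint through discontinuation, intervention or judgment and never through its grade, and nothing in the analysis plan recovers those left out. The size is unknown. The risk is greatest in cohorts 1 and 2 with active disease or MRD, and smaller in maintenance and cohort 3.

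The conclusion rests on two readings: that the three conditions in 8.2.7 are exhaustive, and that the tabulated safety outcome in section 7 means recorded AEs. It does not touch the primary endpoints. Nor does it imply that every low count is drug toxicity: in cohorts 1 and 2 some are due to disease, and counting all of them as effects of SGI-110 would overstate harm. The change is worth making because it is cheap and bears on the main named risk of the drug.

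**What to change.** Keep 8.2.7 for AE entry. Add to sections 7.1 and 7.2:

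- The worst observed CTCAE v4.0 grade per cycle for ANC, platelets, hemoglobin, ALT, bilirubin and creatinine will be derived from all laboratory results obtained under 5.1.1.
- The grades will be tabulated by cohort and disease status (before response or in maintenance), with shift from baseline grade, regardless of action taken, attribution or AE entry.
- The number of blood counts available per cycle will be reported and the rates labelled a lower bound, because mid-cycle counts may have been taken only when clinically indicated.

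Separately, reconcile the related-only rule in 8.1 with the recording grid in 8.2.1.

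The cost is programming and some laboratory data entry, since nothing states that every value reaches the eCRF and responders may have tests done by outside physicians (5.4). No new tests and no change to treatment are needed. The reported hematologic toxicity rate will look less favourable, and in cohorts 1 and 2 it has to be read against disease-related baseline cytopenia, which is why the shift from baseline matters.

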8.3 Reporting of Serious Adverse Events

Any AE that meets any criterion for an SAE requires the completion of an SAE Report Form in addition to being recorded on the AE page/screen of the eCRF. All SAEs must be reported to Astex Drug Safety within 24 hours of the investigator's knowledge of the event by facsimile, or other appropriate method, using the SAE Report Form, or approved equivalent form. This instruction pertains to initial SAE reports as well as any follow-up reports.

The investigator is required to ensure that the data on these forms is accurate and consistent. This requirement applies to all SAEs (regardless of relationship to IP) that occur during the study (from the time the subject signs informed consent to 30 days after the last dose of IP), and those made known to the investigator at anytime thereafter that are suspected of being related to IP. Serious AEs occurring prior to treatment but after informed consent will be collected.

The SAE report should provide a detailed description of the SAE and include a summary of hospital records and other relevant documents. If a subject died and an autopsy has been performed, copies of the autopsy report and death certificate are to be sent to Astex Drug Safety as soon as these become available. Any follow-up data will be detailed in a subsequent SAE Report Form, or approved equivalent form, and sent to Astex Drug Safety.

8.4 Discontinuations

The following events are considered sufficient reasons for discontinuing a subject from study treatment:

- Disease progression and/or no response within the first 6 cycles of SGI-110 in addition to DLI as described in sections 4.2 and 6.0.
- Related and unexpected serious Adverse event(s)
- Development of grade III/IV acute GVHD or severe chronic GVHD
- Subject should receive the subsequent cycle within 70 days after the preceding cycle in cohort 2 and 3. If subject on cohort 2 and 3 cannot receive the subsequent cycle in 70 days, subject will be discontinued from study treatment.

- For patients on cohort 1, treatment cycles in the presence of disease (morphological relapse) can be delayed and subsequent cycles can be given at longer intervals at the discretion of treating physician and principal investigator.
- Withdrawal of consent
- Death
- Lost to follow up
- The investigator determines that the discontinuation of treatment is in the best interest of the patient.
- · 60 days after the last cycle.

Although disease recurrence or progressive disease is considered a sufficient reason for discontinuing a subject from the study treatment, the investigator should consider continuing to treat the subject in attempt to hold the disease until the investigator has alternative therapies and considers the study treatment to be no longer beneficial to the subject, or the rapidity of change of disease state renders it unacceptable for further treatment in the judgment of the investigator.

The reason for discontinuation will be recorded in the eCRF and in the source document for all dosed subjects.

All subjects discontinued from study treatment for any reason will be followed further for GVHD status, progression to AML, and survival. Every attempt should be made to collect all data during the follow-up period unless subjects discontinue from the study.

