- 4.2.1.11 Treatment with SGI-110 will be stopped at any time point if patients exhibit evidence of treatment failure, disease progression, experience of unacceptable toxicity, or the investigator determines that the discontinuation of treatment is in the patient's best interest as provided in Section 6.0.
- 4.2.2. Cohort 2: Patients without morphological evidence of relapse but with minimal residual disease.
 - 4.2.2.1 The enrolled patients will start treatment at the dose level 1 which is 40 mg/m2 SC daily, days 1 to 5. Treatment delays up to 70 days are allowed.
 - 4.2.2.2 The response assessments schedule will be as follows:
 - 4.2.2.2.1 The first response assessment will be performed after the second cycle of SGI-110 given prior to initiation of third cycle.
 - 4.2.2.2.2 For patients who have persistency of detectable MRD after the second cycle of SGI-110 and continue to receive SGI-110 the next assessment will be performed after the fourth cycle.
 - 4.2.2.3 For patients who have persistency of detectable MRD after the fourth cycle of SGI-110 and continue to receive SGI-110 the next assessment will be performed after the sixth cycle.
 - 4.2.2.2.4 Patients may have an earlier disease assessment rather than the indicated time point in the study protocol at the discretion of the treating physician and principal investigator.
 - 4.2.2.3 If patients still have detectable MRD even after the fourth cycle of SGI-110, further treatment (maximum two more cycles) with SGI-110 will be given only if the patient, treating physician and principal investigator determine such an action as the best interest of the patient.
 - 4.2.2.4 Patients who are documented to have no detectable MRD at any time point while treated with SGI-110 will continue the study drug as maintenance therapy at subsequent cycles after documentation of MRD negative status.
 - 4.2.2.5 The dose level of SGI-110 can be increased at least one dose level at the discretion of treating physician and principal investigator if persistency of MRD is documented at any time point of disease assessment while on study.
 - 4.2.2.6 For patients with detectable minimal residual disease at study entry, treatment with SGI-110 will be continued until treatment failure or for a

- maximum of 12 cycles if they have become negative for minimal residual disease at any time point within the first 6 cycles of study drug.

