- 4.2.2.7 Treatment with SGI-110 will be stopped at any time point if patients exhibit evidence of treatment failure, disease progression, experience of unacceptable toxicity, or the investigator determines that the discontinuation of treatment is in the patient's best interest as provided in Section 6.0.
- 4.2.3. Cohort 3: High risk AML and MDS patients who are in complete remission morphologically with no evidence of minimal residual disease by flow cytometry or cytogenetic or molecular testing after allogeneic stem cell transplantation.
 - 4.2.3.1 The enrolled patients will start treatment at the dose level -1 which is 30 mg/m2 SC daily, days 1 to 5 for each 28-day treatment cycle.
 - 4.2.3.2 Treatment delays up to 70 days will be allowed.
 - 4.2.3.3 The response assessments will be performed per departmental guidelines which is day +100, 6th month, 1- year after allogeneic stem cell transplantation.
 - 4.2.3.4 Disease assessment can be done at any time point after transplantation if it is deemed indicated by the treating physician and/or principal investigator.
 - 4.2.3.5 The dose level of SGI-110 can be increased at least one dose level at the discretion of treating physician and principal investigator if deemed in the best interest of the patient by the treating physician and/or principal investigator.
 - 4.2.3.6 For patients who remain in remission without detectable minimal residual disease at study entry, treatment with SGI-110 will be continued until treatment failure or for a maximum of 12 cycles.
 - 4.2.3.7 Treatment with SGI-110 will be stopped at any time point if patients exhibit evidence of treatment failure, disease progression, experience of unacceptable toxicity, or the treating physician and/or principal investigator determines that the discontinuation of treatment is in the patient's best interest as provided in Section 6.0.
- 4.2.4 **Cross-over.** Patients treated on cohort #2 (patients with minimal residual disease while in morphological remission and cohort #3 (maintenance treatment cohort) will be allowed to receive higher doses of SGI-110 if they progress while on therapy with the study drug. Patients who are considered for cross-over to another study cohort due to progression of disease with an aim to receive higher doses of SGI-110 will be screened for the eligibility of that study cohort prior to initiation of higher doses of study drug.
- 4.3 SGI-110 Reconstitution and Administration

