7.1 Cohort 1 and 2: The same phase IIA design will be used for cohort 1 and 2, as follows: A response probability of .20 or larger will be considered promising. A maximum of 25 patients with will be treated in each group. Accrual will be stopped due to futility if less than or equal to 0/8 or 1/20 responses are observed. A patient may have therapy temporarily postponed for up to 56 days due to toxicity. Any patient whose therapy has been started and later permanently discontinued due to the following will be counted as a treatment failure, that is, a non-responder: 1) progressive disease, or 2) due to death, or 3) dropout, or 4) physician decision that it is futile to continue, or 5) severe toxicity prior to achieving disease remission. Patients who do not complete the first cycle of treatment will be considered as non-evaluable. Secondary outcomes will include disease-free survival (DFS) time, overall survival (OS) time, graft-versus-host disease, safety and duration of remission. Within each subgroup (MRD and REL), these events will be tabulated and the distributions of DFS and OS time estimated using the method of Kaplan and Meier (42).

Patients with MRD. In this subgroup, response will be defined as resolution of MRD, at any time point within the first 6 cycles of SGI-110 treatment. A response probability of .20 or larger will be considered promising. A maximum of 25 patients with MRD will be treated. Denoting p = Pr(response), it will be assumed that p follows a beta(.20, .80) prior. Accrual will be stopped due to futility if Pr(p > .20 | data) < .02. This implies that accrual of patient with MRD will be stopped with SGI-110 declared not promising in these patients if less than or equal to 0/8 or 1/20 responses are observed. If necessary, accrual will be suspended after 8 or 20 patients have been treated in order to apply the stopping rule. For example, if there have been 0/7 responses and patient #8 has been treated but not yet been fully evaluated at 4 months, then accrual will be suspended until that patient's outcome has been evaluated. If patient #8 has a response, then patients #9 - #20 may be treated. If patient #8 does not have a response, then accrual of

MRD patients will be terminated. The operating characteristics of this rule are as follows. Computations were carried out in Multc99.

Table 1. Operating characteristics of the rule for monitoring response in MRD patients.

True Pr(Response)	Prob(Stop early)	Achieved Sample Size Quartiles

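### Sections 4.2 and 8.4 conflict on treatment after progression, and 7.1 does not say how a cohort 1 or 2 remission after progression is scored

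*Combined protocol and SAP*

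**What the plan says.** **Treatment after progression.** Sections 4.2.1.11, 4.2.2.7 and 4.2.3.7 share the same opening for the three cohorts: "Treatment with SGI-110 will be stopped at any time point if patients exhibit evidence of treatment failure, disease progression", followed by other reasons. Section 8.4 treats progression as a permitted reason to stop, not a mandatory one: "Although disease recurrence or progressive disease is considered a sufficient reason for discontinuing a subject from the study treatment", it says, "the investigator should consider continuing to treat the subject in attempt to hold the disease". Section 4.2.4, repeated in 7.3, adds that patients in cohorts 2 and 3 "will be allowed to receive higher doses of SGI-110 if they progress while on therapy with the study drug", after screening for eligibility in the other cohort.

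**Scoring in cohorts 1 and 2.** Section 7.1 provides: "Any patient whose therapy has been started and later permanently discontinued due to the following will be counted as a treatment failure". Progressive disease is the first reason listed. For the MRD cohort, "response will be defined as resolution of MRD, at any time point within the first 6 cycles of SGI-110 treatment". For the relapse cohort, response is disease remission within the same six cycles. Neither definition requires the response to come before progression. Section 6.3 defines progression but does not connect it to the scoring of response.

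**Cross-over.** Section 7.3 follows cross-over patients for later outcomes, including response and survival, from the date of cross-over. It does not say what is recorded for them in the cohort they entered.

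**The concern.** There are two linked problems.

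First, the treatment instructions disagree. One part of the plan requires a stop at progression, and another asks the investigator to think about continuing. No passage says which prevails.

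Second, the primary endpoint of cohorts 1 and 2 inherits the disagreement. The failure rule is triggered by permanently ending therapy because of progression, not by progression itself. Two patients with the same disease course can thus be scored differently because one investigator stopped and another did not. Each cohort has at most 25 patients, and the futility bounds are 0/8 and 1/20, so a single patient's classification can decide whether accrual goes on.

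**Working it through.** **1. One disease course, several routes.** Take a cohort 2 patient with morphologic relapse after cycle 2 (progression under 6.3.2) who has no detectable MRD by cycle 6.

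| Route | Text that applies | Scoring in cohort 2 |
|---|---|---|
| Stopped at progression | 4.2.2.7, then the 7.1 failure rule | Non-responder |
| Continues without cross-over | 8.4; therapy not permanently discontinued for progression | Failure rule not triggered; response definition met |
| Crosses over to a higher dose | 4.2.4 and 7.3 | Later outcomes followed from cross-over; cohort 2 result not stated |

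The first two routes also exist in cohort 1, where progression is marrow blasts above 60% and/or new extramedullary sites (6.3.1). They do not create the problem in cohort 3: section 7.2 defines the RFS time as time to progression or death, so the event is recorded whether or not dosing continues.

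**2. The plan's own figures.** Inputs from 7.1: prior beta(.20, .80); stop if Pr(p > .20 | data) < .02; bounds 0/8 and 1/20; maximum 25 patients. With x responses in n patients,

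Pr(p > .20 | x, n) = 1 − F(.20; .20 + x, .80 + n − x), where F is the beta distribution function.

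- 0/7 gives .0206 (continue) and 0/8 gives .0153 (stop).
- 1/19 gives .0223 (continue) and 1/20 gives .0180 (stop).

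Both bounds reproduce. With looks at 8 and 20,

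Prob(stop early) = (1 − p)^8 + 8p(1 − p)^7 × (1 − p)^12 = (1 − p)^8 + 8p(1 − p)^19.

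At p = .05 this is .6634 + .1509 = .814. At .10, .15 and .20 it gives .539, .327 and .191. Table 1 states .82, .54, .32 and .18. All agree within 2 points, so Table 1 is not in dispute.

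**3. One patient at a futility look.** Suppose one remission after progression is counted as a response.

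| Look | Not counted | Counted |
|---|---|---|
| 8 patients | 0/8: .015, stop | 1/8: .227, continue |
| 20 patients | 1/20: .018, stop | 2/20: .090, continue |

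**4. Range.** The documents give no rate of remission after progression. As an assumption, let such remissions add 2, 5 or 10 percentage points to the rate that would be counted if response had to precede progression (the strict rate). Using the formula in step 2, Prob(stop early) becomes:

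| Strict rate | None added | +2 points | +5 points | +10 points |
|---|---|---|---|---|
| .05 | .81 | .70 | .54 | .33 |
| .10 | .54 | .44 | .33 | .19 |
| .15 | .33 | .26 | .19 | .11 |

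These values show sensitivity only; they do not estimate what will happen.

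**5. At full enrolment.** One patient is 1/25 = 4 percentage points. The posterior is .268 at 4/25 and .461 at 5/25. Both are far above .02, and the plan sets no success threshold at 25 patients, so no decision changes.

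**The case against.** **Section 7.1 may intend every progressor to be a failure.** It names progressive disease first among the reasons for non-response and never says that a progressor who stays on drug is not a failure. A reader might infer that 7.1 positively counts remissions after progression as responses. The text does not go that far: it is silent on the order of the two events. The silence stands, and if failure is the intent, the added sentence changes no result.

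**Section 7.3 deals with cross-over.** A reader might infer that remissions reached at another cohort's dose enter the entry cohort's rate. Section 7.3 points the other way, because it treats these patients as a subgroup with its own time origin. This largely answers the cross-over route. What remains is that 7.3 does not fix the entry-cohort result, and it covers neither cohort 1 nor continuation under 8.4 without cross-over.

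**The remaining route is narrow.** Section 8.4 describes holding the disease until alternatives are available, and a cohort 1 patient would have to remit after exceeding 60% blasts or developing new extramedullary disease, all within six cycles. Sections 5.3.4 and 5.3.5 also schedule the later marrows only in the absence of progression. That is fair on frequency. However, 5.3.7, 4.2.1.2.4 and 4.2.2.2.4 allow other assessments. Section 2.8 says that responses to DLI usually appear within two to three months and a full response can take a year or longer, while section 4.6.3 plans the first DLI for cycle 2. Late remission therefore cannot be ruled out.

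**Any reclassified patient at a boundary would reverse a stop.** True, but here the reclassification would follow from a choice the plan leaves to the investigator.

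**Conclusion.** The point holds in a limited form. The treatment passages conflict and must be reconciled. In cohorts 1 and 2, the primary response can be scored either way for a patient who progresses, continues and later remits. Cohort 3 shares only the conflict of wording.

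The direction of any bias is upward, since counting remissions after progression can only add responses. Its size is unquantified, and a reader should not take it as demonstrated: it depends on how often patients continue after progression and then remit, and the documents report neither. The only decision at risk is a futility stop, which one such patient reverses at 0/8 or at 1/20.

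A reader might also infer that moving from 4/25 to 5/25 (16% to 20%) crosses a line for declaring the treatment promising. The documents do not support this. In 7.1 the value .20 refers to the true response probability used in the futility rule, not to a cut-off for the observed proportion.

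**What to change.** - **Section 7.1:** state that, for cohorts 1 and 2, progression as defined in 6.3 before a response makes the patient a non-responder in the entry cohort, whether or not SGI-110 continues or the patient crosses over.
- **Later remissions:** report them separately; for cross-over patients, within the subgroup already described in 7.3.
- **Sections 4.2.1.11, 4.2.2.7, 4.2.3.7, 4.2.4, 7.3 and 8.4:** reconcile the text on treatment after progression. Which clinical rule applies is for the sponsor to decide, and the scoring sentence works under either.

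The cost is one sentence in the statistical section and a wording amendment, with no change to sample size, stopping bounds or Table 1. The downside is that the reported response rate may be slightly less favourable.
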